1.2. Study Design

This is a Phase 2, randomized, double-blind, parallel-group, placebo-controlled, multicenter study to evaluate the efficacy and safety of ALXN2050 in adult participants (\geq 18 years of age at the time of signing the informed consent form [ICF]) diagnosed with gMG with a Myasthenia Gravis Foundation of America (MGFA) Clinical Classification between Class II to IV at the Screening Visit and an MG-ADL total score \geq 5 (with at least 50% of the score attributed to nonocular elements) at the Screening Visit and at randomization (Day 1).

Approximately 70 eligible participants will be stratified by the MG-ADL total score at Baseline $(<7 \text{ versus} \ge 7)$ and randomized on Day 1 in a 2:1:2 ratio to 1 of 3 treatment groups: ALXN2050 180 mg twice daily bid (Group 1), ALXN2050 120 mg bid (Group 2), or placebo (Group 3). Participants will receive the study intervention bid from Day 1 through Week 117.

Participants randomized to Group 1 and Group 2 will receive ALXN2050 during the PEP (8 weeks) and the ETP (26 weeks). Participants in Group 3 will receive placebo treatment during the PEP and will be rerandomized in a 1:1 ratio to receive either ALXN2050 180 mg bid (Group 3a) or ALXN2050 120 mg bid (Group 3b) at the end of the PEP. During the OLE Period (up to approximately 1.5 years), all participants will receive ALXN2050 and will be switched to the optimal dose of ALXN2050 if that dose has been identified during the study, as long as the participant has completed the first 34 weeks of treatment.

The study consists of a Screening Period of up to 4 weeks, a PEP of 8 weeks, an ETP of 26 weeks, and an OLE Period of up to approximately 1.5 years. An EOS Visit will occur 30 days after the last dose of study intervention for all participants. The overall study duration for an individual participant will be approximately 125 weeks. A schematic of the study design is included as Figure 1.

[figure not shown]

Figure 1: ALXN2050-MG-201 Study Design Schematic

Note: Participants randomized to placebo will only receive placebo for 8 weeks during the study. Abbreviations: bid = twice daily; EOS = end of study; N = number of participants

2. STATISTICAL HYPOTHESES

2.1. Primary Hypothesis

The primary hypothesis is that the ALXN2050 180 mg bid group is superior to the placebo group in the proportion of responders in the primary endpoint. The responders are defined as participants who achieved an MG-ADL total score reduction of at least 2 points in any 4 consecutive weeks during the first 8 weeks of the PEP and who received no rescue therapy. The hypothesis for assessing superiority with respect to the proportions of responders is as follows:

$$H_0:P_3-P_1\leq 0;\ H_1:P_3-P_1>0$$

where p_1 and p_3 are the proportions of responders in the primary endpoint for the placebo and ALXN2050 180 mg bid groups, respectively.

2.2. Secondary Hypothesis

The secondary hypothesis is that there is an increasing trend in the proportions of responders in the primary endpoint among the 3 treatment groups. The hypothesis for assessing the increasing trend is as follows:

 $H_0: P_1 = P_2 = P_3; H_1: P_1 \le P_2 \le P_3$; with at least 1 strict inequality

where p₁, p₂, and p₃ are the proportions of responders in the primary endpoint in the placebo group, ALXN2050 120 mg bid group, and ALXN2050 180 mg bid group, respectively.

3. SAMPLE SIZE DETERMINATION

The study has 3 treatment groups: ALXN2050 180 mg bid, ALXN2050 120 mg bid, and placebo. The goals of this study are to establish proof of concept for the treatment of gMG with ALXN2050 and to select a dosage for further development of ALXN2050 in gMG. For sample size determination, both trend analyses among the 3 treatment groups and differences in proportions of responders between the ALXN2050 180 mg bid group and the placebo group in the primary endpoint are used.

Data from the Argenx ADAPT study and the Momenta Vivacity-MG study were used to estimate the response rate on placebo with background standard-of-care treatment. Based on the data from both studies, the response rate for the placebo group is assumed to be 25%. A sample size of 54 evaluable participants with a randomization ratio of 1:1 to the placebo group and the ALXN2050 180 mg bid group results in approximately 80% power to detect a treatment effect (difference in the proportions of responders) of 35% between the 2 treatment groups, using a 2-sided type I error rate of 0.1 and the exact binomial computation method. An additional 13 evaluable participants will be enrolled to the ALXN2050 120 mg bid group for a total of 67 evaluable participants.

Assuming that the response rate for the ALXN2050 120 mg bid group is 45%, with a total of 67 evaluable participants, the study has approximately 80% power to detect the increasing trend in the proportions of responders using the Cochran Armitage test at a 2-sided type I error rate of 0.1.

Assuming approximately 5% non-evaluability, the study is planned to enroll 70 participants in total. The sample size calculations were performed in PASS 2020.

4. ANALYSIS SETS

| Analysis Set | Description |
|---------------------------------|---|
| Randomized Set | All randomized participants grouped by randomized treatment group. |
| Re-randomized Set | All re-randomized placebo arm (Group 3) participants grouped by re- randomized treatment group. |
| Full Analysis Set (FAS) | All randomized participants who received at least 1 dose of the study intervention and have a baseline and at least 1 postbaseline efficacy assessment. Participants will be analyzed as randomized. |
| PK Analysis Set | All randomized participants who have a baseline PK assessment and at least 1 evaluable postdose PK assessment. |
| PD Analysis Set | All randomized participants who have a baseline PD assessment and at least 1 evaluable postdose PD assessment. |
| Per Protocol Set (PPS) | All participants in the FAS without important protocol deviations. See Section 6.2.2 for the list of important protocol deviations. |
| Safety Set (SS) | All randomized participants who received at least 1 dose of the study intervention. Participants will be analyzed according to the study intervention they actually received. (Study intervention received is the same as planned study intervention if the participant has received at least 1 dose of planned study intervention. If planned study intervention is not received at all, the most frequently received study intervention will be the received study intervention). |
| ALXN2050-Treated Set | All randomized participants who received at least 1 dose of the ALXN2050. Participants will be analyzed according to the study intervention they actually received. (Study intervention received is the same as planned study intervention if the participant has received at least 1 dose of planned study intervention. If planned study intervention is not received at all, the most frequently received study intervention will be the received study intervention). |
| Open-label Extension Set (OLES) | All randomized participants who received at least 1 dose of ALXN2050 during the OLE Period. |

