- p The MG-ADL is required to be performed first, followed by the QMG. The MG-ADL assessment should be performed by a properly trained Clinical Evaluator (preferably the same evaluator) throughout the study. The recall period for MG-ADL is the preceding 7 days or since the last visit if the visit interval is less than 7 days.
- q C-SSRS will be assessed for both lifetime and past 12 months at Baseline, and Since Last Visit for subsequent visits.
- r The abbreviated physical examination will be performed, if necessary, on the basis of the participant's health status and the clinical judgment of the Investigator.
- s A symptom based neurologic examination should be performed if the participant has any complaints or clinical findings attributable to the central nervous system and if positive for findings, a full neurologic examination will need to be performed at that assessment time point and at future time points as needed (determined by the Investigator).
- t Vital sign measurements will include systolic and diastolic blood pressure (millimeters of mercury [mmHg]), heart rate (beats/minute), and temperature (degrees Celsius [°C] or degrees Fahrenheit [°F]). On dosing days, vital signs will be taken before study intervention administration and after the participant has been resting for at least 5 minutes.

 Table 2:
 Schedule of Activities (Screening and Primary Evaluation Periods)

- u Participants will be given a safety card prior to the first dose of study intervention. At each visit throughout the study, investigational site staff will ensure that the participant has the safety card and will review the guidelines with the participant.
- v Safety laboratory samples will be analyzed by the central laboratory. A list of parameters that will be obtained during the study are provided in Table 11.
- w Baseline and trough blood samples for serum PK will be collected predose (within 30 minutes prior to the administration of study intervention). Peak blood samples for serum PK/PD are to be taken  $2 \pm 0.5$  h and  $4 \pm 0.5$  h postdose. All collection times will be recorded in the participant's electronic case report form.
- x Trough (within 30 minutes predose) and peak ( $2 \pm 0.5$  h and  $4 \pm 0.5$  h postdose).
- y Trough (within 30 minutes predose).

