## 9.3. **Populations for Analyses**

For the purpose of analyses, the following populations are defined. The primary efficacy analyses will be based on the FAS and safety analyses will be based on the SS.

Population	Description
Randomized Set	All randomized participants grouped by randomized treatment group.
FAS	All randomized participants who receive at least 1 dose of study intervention and have a baseline and at least 1 postbaseline efficacy assessment. Participants will be analyzed as randomized.
PK Analysis Set	All randomized participants who have a baseline PK value and at least 1 evaluable postdose PK assessment.
PD Analysis Set	All randomized participants who have a baseline PD value and at least 1 evaluable postdose PD assessment.
PPS	All participants in the FAS without any important protocol deviations.
SS	All randomized participants who receive at least 1 dose of study intervention. Participants will be analyzed according to the study intervention they actually received.
OLE Set	All randomized participants who receive at least 1 dose of ALXN2050 at the start of the OLE Period.

Abbreviations: FAS = Full Analysis Set; OLE = Open-label Extension; PD = pharmacodynamic; PK = pharmacokinetic; PPS = Per Protocol Set; SS = Safety Set

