5.7. Other Analyses

5.7.1. PK Analyses

For both of Analysis 1 (Week 8) and Analysis 2 (Week 34), the SS will be used for PK concentration listings and individual figures, and the PK set will be used for PK parameter listings, all summary tables, and mean figures.

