5.7.1.2. Plasma PK Concentrations

Blood samples for the analysis of concentrations of ALXN2050 in plasma for each of the treatments will be collected at the following timepoints:

- PEP of 8 weeks (Day 1 to Week 8): predose on Days 1, 29, and 57 and at 2 and 4 hours postdose on Days 1 and 57.
- ETP of 26 weeks (Weeks 9 to 34): predose on Days 85, 113, 183, and 239 and at 2 and 4 hours postdose on Days 85 and 113.

Available individual plasma concentrations of ALXN2050 for each treatment, at the time of each analysis, will be presented in data listings and summarized separately using descriptive statistics (N, n [nonmissing values within the population], arithmetic mean, SD, CV percentage [CV%], median, minimum, and maximum) by period (PEP and ETP), treatment group, day, and scheduled timepoint. Individual plasma concentrations of ALXN2050 will be plotted for each participant by actual time (in days) continuous for both periods on both linear and semilogarithmic scales. Mean plasma concentrations of ALXN2050 versus nominal time (in days) will be plotted continuous for both periods on both linear and semilogarithmic scales and with actively treated groups overlayed on the same plot.

Plasma PK concentrations of ALXN2050 will be reported to 3 significant figures in summary statistics except for CV%, which will be reported to 1 decimal place, and N and n, which will be reported as an integer.

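### The PK Analysis Set requires a baseline PK sample that no planned PK summary uses, so one missed Day 1 predose draw removes a participant from all PK summary tables and mean figures through Week 34

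*SAP*

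**What the plan says.** SAP Section 4 opens its definition of the PK Analysis Set with "All randomized participants who have a baseline PK assessment" and adds a second condition, one or more evaluable PK assessments after dosing. Protocol Section 9.3 sets the same two conditions in slightly different words: "All randomized participants who have a baseline PK value and at least 1 evaluable postdose PK assessment".

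SAP Section 5.7.1 divides the PK outputs between two sets. For one part, "the SS will be used for PK concentration listings and individual figures", with SS meaning the Safety Set. For the rest, "the PK set will be used for PK parameter listings, all summary tables, and mean figures".

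SAP Section 5.7.1.2 gives the sampling times. In the Primary Evaluation Period (PEP) they are "predose on Days 1, 29, and 57 and at 2 and 4 hours postdose on Days 1 and 57". In the Extended Treatment Period (ETP) they are "predose on Days 85, 113, 183, and 239 and at 2 and 4 hours postdose on Days 85 and 113". The protocol's schedules of activities (Tables 2 and 3) agree for the PEP but show no postdose PK samples at Day 85. Table 2 shows no PK sample at Screening and allows 30 minutes before dosing for the Day 1 baseline draw.

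The SAP addendum drops the PK parameters and the population PK and exposure-response work. It keeps all other PK analyses and leaves the PK Analysis Set unchanged.

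**The concern.** A baseline condition makes sense where the outcome is a change from baseline, as it is for the PD measures. PK concentrations are not analysed that way. They are summarised by timepoint, and the only planned parameters, Cmax and Ctrough, are observed values.

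The baseline value itself should be uninformative for these summaries. Exclusion criterion 20 bars any earlier complement inhibitor, protocol Section 2.2.2 describes ALXN2050 as an inhibitor of complement factor D, and SAP Section 5.7.1.1 counts values below the limit of quantification as 0.

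The condition can therefore take usable trough and peak concentrations out of the group summaries without improving them. Characterising PK is a stated objective. Protocol Section 4.3 reports large variability in PK and gives it as a reason for studying the higher dose. With about 14 participants on 120 mg in the PEP, each one lost affects the descriptive mean, SD and CV%.

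**Working it through.** The plan states no figure on this point, so there is nothing to reproduce. The check is one of logic, followed by simple counts.

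**Which sample can serve as baseline.** Protocol Section 9 and SAP Section 5.1 place baseline at or before the first dose. Day 1 predose is the only scheduled PK sample that qualifies, and there is no Screening sample to fall back on.

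**Whether any PK output uses it.** SAP Sections 5.7.1.2 and 5.7.1.3 list concentrations by period, group, day and timepoint, then Cmax and Ctrough. None is baseline-adjusted. The Day 1 predose value is one row of the concentration table and nothing more. By contrast, SAP Section 5.7.2.2 analyses the PD measures as change from baseline.

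**Samples left out of the summaries per missed draw** (Clinical Deterioration visits not counted):

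- PEP, both documents: 3 predose + 2 × 2 postdose = 7.
- ETP, SAP: 4 predose + 2 × 2 postdose = 8. Total 7 + 8 = 15, so 15 − 1 = 14 others are left out.
- ETP, protocol Table 3: 4 predose + 2 postdose (Day 113 only) = 6. Total 7 + 6 = 13, so 13 − 1 = 12 others are left out.

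**Share of an arm per missed draw.** About 70 participants in a 2:1:2 ratio gives 70 × 2/5 = 28 on 180 mg, 70 × 1/5 = 14 on 120 mg and 28 on placebo. One miss is 1/14 = 7.1% of the 120 mg arm or 1/28 = 3.6% of the 180 mg arm. These are shares per event, not expected losses.

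**Expected loss.** The rate *m* of a missed Day 1 predose draw is not in the documents, so a range of 1% to 10% is assumed, with misses independent between participants. Expected exclusions are *n* × *m*, and the chance of at least one is 1 − (1 − *m*)^*n*.

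| Assumed *m* | 120 mg (*n* = 14): expected; chance of at least one | 180 mg (*n* = 28): expected; chance of at least one |
|---|---|---|
| 1% | 0.14; 13.1% | 0.28; 24.5% |
| 5% | 0.7; 51.2% | 1.4; 76.2% |
| 10% | 1.4; 77.1% | 2.8; 94.8% |

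**Placebo participants who cross over.** SAP Section 5.1.2 assigns the PEP baseline to Groups 3a and 3b (about 28/2 = 14 each) in nonefficacy analyses. SAP Section 5.7.1 names no PK baseline of its own. If the PEP rule applies, a draw missed before the first placebo dose also removes these participants' later active-treatment concentrations from the summaries.

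**After the change.** With the baseline condition deleted, exclusions caused only by a missed Day 1 predose draw are 0 at every *m*.

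**The case against.** A reader might infer that one missed draw removes all of a participant's PK data. The documents do not support that. SAP Section 5.7.1 keeps the concentration listings and individual figures on the Safety Set, which has no PK condition. SAP Section 5.7.3 places population PK and exposure-response in a separate analysis without tying it to the PK Analysis Set. The data are omitted from the group summaries, not discarded.

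Three further points stand in whole or in part:

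- **Frequency is unknown.** Day 1 is a clinic visit with the first dose given on site, and PD and biomarker samples are drawn predose the same day. Misses may be rare or absent, and the 1% to 10% range is an assumption.
- **Nothing inferential depends on the set.** Its outputs are descriptive. The exposure-response work intended to inform dose selection was not linked to it, and the addendum has since cancelled that work and the PK parameters. This keeps the point minor, but the concentration summaries that remain are still governed by the definition.
- **The predose value is not worthless.** No passage states that it is zero. It is a planned timepoint, and an unexpected positive value could reveal a sample mix-up or assay interference. That is a reason to draw and list the sample. It is not a reason to make it a condition of entry for every later timepoint.

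**Conclusion.** The point holds as a minor flaw in a set definition. A participant missing only the Day 1 predose draw is left out of all PK summary tables and mean figures through Week 34, and of PK parameter listings where produced, for no analytic gain. The effect is confined to those descriptive outputs.

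The conclusion rests on three things: the inference that participants are ALXN2050-naive, arm sizes of 14 and 28 taken from the planned 70, and an assumed miss rate, without which only the per-event shares can be stated. The extension to Groups 3a and 3b depends on the PEP baseline rule being applied to PK.

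There is also a small ambiguity between the documents. The protocol asks for a baseline value and the SAP for a baseline assessment, so it is unclear whether a sample that was drawn but could not be analysed would qualify.

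**What to change.** Delete the baseline condition from the PK Analysis Set in protocol Section 9.3 and SAP Section 4, using the same words in both. The set becomes all randomized participants who took at least one dose of study intervention and have at least one evaluable PK concentration after dosing. This also removes the value-or-assessment ambiguity.

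The dose condition should refer to study intervention, not to ALXN2050. The present set includes placebo participants, and requiring an ALXN2050 dose would drop those who stop before Week 8.

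Keep the baseline condition for PD, where change from baseline needs it. The Day 1 predose PK sample can still be drawn and reported.

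The cost is a short edit. Because the addendum follows the Week 8 results, the change to the set should be recorded openly in the SAP or its addendum. No hypothesis test or power figure changes.

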5. STATISTICAL ANALYSES

5.1. General Considerations

Summary statistics will be computed and displayed by visit, by treatment group, and overall, where applicable. The summary statistics for continuous variables will include, but will not be limited to, the number of participants, mean, SD, minimum, median, and maximum. For categorical variables, frequencies and percentages will be presented.

Inference from efficacy analyses will be based on a 2-sided type I error rate of 10% unless stated otherwise. No multiplicity adjustment will be implemented. Statistical analyses will be performed using the Statistical Analysis Software (SAS[®]) Version 9.4 or higher.

Medications will be coded using the World Health Organization Drug Dictionary (WHO DD; March 2021 or higher). Therapies will be coded using Medical Dictionary for Regulatory Activities (MedDRA; Version 24.0 or higher).

AEs will be coded by primary System Organ Class (SOC) and Preferred Term (PT) using MedDRA (Version 24.0 or higher).

5.1.1. Data Presentation for the First Analysis at Week 8

Data summaries for the analyses on the PEP data will be presented by 3 treatment groups ("Group 1: ALXN2050 180 mg bid", "Group 2: ALXN2050 120 mg bid" and "Group 3: Placebo"). Baseline is defined as the last measurement on or prior to the first dose of study intervention. For analysis including data beyond week 8, data summaries will be presented by 5 treatment groups ("Group 1: ALXN2050 180 mg bid", "Group 2: ALXN2050 120 mg bid", "Group 3: Placebo", "Group 3a: ALXN2050 180 mg bid" and "Group 3b: ALXN2050 120 mg bid"). Placebo group may be dropped for some of the analyses as specified in the respective sections. For all groups other than Groups 3a and 3b, baseline is defined as the last measurement on or prior to the first dose of study intervention. For Group 3a and 3b, two baselines will be defined for efficacy analysis: the PEP baseline is defined as the last measurement on or prior to the first dose of the PEP (primary baseline) and the ETP baseline is defined as the last measurement on or prior to the first dose of the Group 3a and 3b.

5.1.2. Data Presentation for the Second Analysis at Week 34

Data summaries for the exploratory, safety, biomarker, and PK/PD analyses will be presented by 5 treatment groups. Placebo group may be dropped for some of the analyses as specified in the respective sections. For all groups other than Group 3a and 3b, baseline is defined as the last measurement on or prior to the first dose of study intervention. For Group 3a and 3b, 2 baselines will be defined for efficacy analysis: the PEP baseline is defined as the last measurement on or prior to the first dose of the PEP (primary baseline) and the ETP baseline is defined as the last measurement on or prior to the first dose of the ETP (secondary baseline). The PEP baseline will be used in nonefficacy analysis for Group 3a and 3b.

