#### Table 3: Schedule of Activities (Extended Treatment Period)

Period	Extended Treatment Period a												
Study Year					Y	ear 1							
Study Day (D)	D64	D71	D78	D85	D92	D99	D106	D113	D183	D239	ED b	CDc	EOS b
Study Week (W)	W9	W10	W11	W12	W13	W14	W15	W16	W26	W34	NA	NA	NA
Visit Type	Phone call	Phone call	Phone call	In- clinic	Phone call	Phone call	Phone call	In- clinic	In- clinic	In- clinic	In- clinic	In- clinic	In- clinic
Study Window (days)	NA	NA	NA	±3	NA	NA	NA	±3	±3	±3	NA	NA	±2
Safety Laboratory Tests o													
Serum pregnancy p											Х		Х
Urine pregnancy p				Х				Х	Х	Х		Х	
Clinical chemistry				Х				Х	Х	Х	X	Х	
Hematology				Х				Х	Х	Х	Х	Х	
Coagulation panel				Х				Х	Х	Х	Х	Х	
Urinalysis				Х				Х	Х	Х	Х	Х	
PK/PD Tests q													
РК				Xr				Xs	Xr	Xr		Xr	
PD: AP activity and Bb t				Х				Х	Х	Х		Х	
Biomarker Tests													
Anti-AChR antibody				Х				Х	Х	Х	X	Х	
Factor D, C3, CP activity, nongenetic exploratory biomarkers (eg, MuSK, LRP4) u				X				х	х	x	Х	X	
Other				Х									
Concomitant medication	X	Х	Х	Х	Х	Х	Х	Х	Х	Х	X	Х	Х
Nonpharmacologic treatments and therapies	Х	Х	Х	Х	Х	X	X	X	Х	X	Х	X	Х

a The ETP begins at the Day 57 (Week 8) Visit after all assessments of the visit are performed, but before the administration of ALXN2050 in the clinic and postdose PK/PD sampling.

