# 6. STUDY INTERVENTION

Study intervention is defined as any investigational intervention(s), marketed product(s), placebo, or medical device(s) intended to be administered to a study participant according to the study protocol.

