5.6.1.3.1. Laboratory Tests

All laboratory data as of the data cutoff date will be included. Absolute values and changes from Baseline in central laboratory parameters (continuous variables) will be summarized descriptively at each visit by treatment group. Baseline is defined as the last nonmissing assessment value prior to the first dose of study intervention for the PEP. Shift tables over time will be presented for all laboratory values, where applicable, using normal, low, or high based on normal range values.

All central laboratory data will be presented in by-participant listings.

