5.6.1.3.3. Electrocardiograms

Descriptive statistics by visit and treatment group will be presented for each ECG parameter (including PR, QRS, QT, corrected QT interval [QTc], and QTc using Fridericia's formula [QTcF]) value and for change from baseline values.

An outlier analysis that will summarize the frequency and percentage of participants who meet any of the following outlier criteria will be performed:

- QT and QTcF interval > 450 msec
- QT and QTcF interval > 480 msec
- QT and QTcF interval > 500 msec
- QT and QTcF interval increases from Baseline > 30 msec
- QT and QTcF interval increases from Baseline > 60 msec

This outlier analysis will be performed for the PEP data only using the SS and separately for the aggregated PEP, ETP, and OLE Period (if applicable) data during the ALXN2050 treatment period using the ALXN2050-Treated Set.

Overall ECG results will also be classified as normal, abnormal not clinically significant, and abnormal clinically significant. A summary table will be provided for clinically significant abnormalities by visit and treatment group.

A by-participant listing of ECG results will be presented.

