5.6.2. Safety Analyses at Analysis 2 (Week 34)

All outputs for safety outcomes during the first 34 weeks and aggregated safety summary, including additional OLE Period data during the ALXN2050 treatment period, will be based on the ALXN2050-Treated Set, unless otherwise specified. Baseline is defined as the last available assessment prior to the first dose of study intervention. Baseline for Groups 3a and 3b is the last available assessment prior to the first dose of study intervention during the PEP.

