5.9. Final Analyses

The final analysis will be conducted at the end of the study. The OLES will be used for the final analysis, unless otherwise specified.

The following efficacy data collected during the OLE Period will be listed and summarized in descriptive statistics by dose level, which is the dose received at the specific visit during the OLE Period:

- Change from Baseline in the MG-ADL total score
- Proportion of participants with at least a 2-, 3-, 4-, 5-, 6-, 7-, or 8-point improvement in the MG-ADL total score
- Change from Baseline in the QMG total score
- Proportion of participants with at least a 3-, 4-, 5-, 6-, 7-, or 8-point improvement in the QMG total score
- MGFA-PIS status
- Change from Baseline in the Neuro-QoL Fatigue total score
- For efficacy and nonefficacy endpoints, baseline is defined as the last measurement on or prior to the first dose of the PEP.

AEs will be analyzed and reported in terms of TEAEs, which are defined as any AEs that started or worsened in severity on or after the first dose of study intervention through 30 days after the last dose of study intervention.

AE data will be listed and summarized in an aggregated manner (combining data from the PEP, ETP, and OLE Period) by dose received using the SS. Additional safety data collected by study visit during the OLE Period will be listed and summarized by dose level, which is the dose received ("ALXN2050 180 mg bid" and "ALXN2050 120 mg bid") at the specific visit during the OLE Period.

Available PK, PD, and biomarker data during the OLE Period will be listed using the OLES.

Description of additional analyses may be provided in a SAP addendum before the conduction of the final analysis.

6. **SUPPORTING DOCUMENTATION**

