1.2. Changes From Analyses Specified in the Previous Version of the SAP

- Primary endpoint: primary endpoint analyses will be performed as described in the SAP Amendment Version 1.0 Section 5.3.2. Sensitivity and supplementary analyses will not be performed.
- Secondary efficacy endpoints: only change from baseline in the QMG total score and change from baseline in the MG-ADL total score as described in the SAP Amendment Version 1.0 Section 5.4.1.1 and Section 5.4.1.3 (excluding the trend analysis to detect dose-response trend) will be performed. Descriptive summary of absolute and change from Primary Evaluation Period (PEP) baseline in MG-ADL and QMG total score will tabulate study visits through the entire study. Supplementary analyses will not be performed.
- PK/PD: PK parameter will not be reported as described in the SAP Amendment Version 1.0 Section 5.7.1.3. Population PK and exposure-response analysis will not be performed as described in the SAP Amendment Version 1.0 Section 5.7.3. All other PK/PD analyses will be performed.
- Biomarker: biomarker analysis will not be performed.
- Safety: All safety analyses will be performed as planned, as described in the SAP Amendment Version 1.0 Section 5.6 with all data collected until the end of study.
- No exploratory endpoint analyses will be performed.
- All other analyses (e.g., demographic, baseline disease characteristics, MG/non-MG medications/therapies, protocol deviation, etc), if not mentioned above, will be performed as planned.

Study exposure and adverse event data summaries will include the following two sets of analyses: (1) summary of the PEP data by Group 1, 2, 3; (2) summary of the ALXN2050 Treated Period data by Group 1, 2, 3a, 3b. Per-protocol Set and Re-randomized Set will be removed.

Medication summaries by treatment group and overall using the number and percentage of participants will be presented by WHO-DRUG Anatomical Therapeutic Chemical Level 3 class code and by WHO-DRUG generic name.

All planned listings other than the ones for exploratory biomarker endpoints will be produced.

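### For placebo participants who cross to ALXN2050 (Groups 3a/3b), laboratory, vital-sign, ECG and PD changes on drug are measured only from the pre-placebo baseline, so they include change over 8 placebo weeks

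*SAP*

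**What the plan says.** For efficacy, SAP 5.1.1 and 5.1.2 give Groups 3a and 3b two baselines. The PEP baseline is taken before placebo starts and is labelled primary. The ETP baseline is secondary, and SAP 5.1.2 takes it at the start of the ETP. For all other data, SAP 5.1.2 allows only the first: "The PEP baseline will be used in nonefficacy analysis for Group 3a and 3b".

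The rule recurs elsewhere in the SAP:

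- Safety at the Week 34 analysis (5.6.2): "Baseline for Groups 3a and 3b is the last available assessment prior to the first dose of study intervention during the PEP". SAP 5.7.2 uses the same sentence for PD.
- Laboratory tests (5.6.1.3.1): "Baseline is defined as the last nonmissing assessment value prior to the first dose of study intervention for the PEP".
- Final analysis (5.9): "For efficacy and nonefficacy endpoints, baseline is defined as the last measurement on or prior to the first dose of the PEP".

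Protocol Section 6 counts placebo as a study intervention, so for these participants the reference value comes before their first placebo dose on Day 1.

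These baselines feed the by-visit change summaries, the laboratory shift tables and the change-based ECG counts, for example "QT and QTcF interval increases from Baseline > 60 msec". SAP 5.6.1.3.3 runs those ECG counts separately for the ALXN2050 treatment period on the ALXN2050-Treated Set. SAP 6.1.2 also defines both baselines for Groups 3a/3b, but does not confine the ETP baseline to efficacy.

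The SAP Addendum (1.2) keeps these outputs for the final report: "Safety: All safety analyses will be performed as planned". It also keeps the PD analyses, dropping only PK parameters and the population PK and exposure-response work.

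**The concern.** A table for the ALXN2050 treatment period should show what changed while participants took ALXN2050. In Groups 3a/3b the reference value is 8 weeks and one whole treatment period too early for that. A laboratory shift or QTcF rise that appeared on placebo and persisted is counted under ALXN2050. A value that fell on placebo and then rose on ALXN2050 may not be counted at all.

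The plan is also uneven for the same participants. SAP 5.6.2.2 dates their treatment-emergent adverse events from the first ETP dose, while their laboratory, vital-sign, ECG and PD changes run from before placebo. At stake is how cleanly the change tables for two of the four ALXN2050-treated groups describe the drug.

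**Working it through.** The plan states no figure on this point, so there is none to reproduce. The check has five steps.

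**1. How many participants.** Protocol 4.1 gives about 70 participants randomized 2:1:2, with the placebo group re-randomized 1:1.

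- Placebo: 70 × 2/5 = 28.
- Groups 3a and 3b: 28/2 = 14 each.
- One participant in a group of 14: 1/14 = 7.1 percentage points.

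The 28 is an upper figure, because anyone who leaves before Week 8 is not re-randomized.

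**2. What the PEP-baseline change contains.**

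Change from PEP baseline = (Week 8 − Day 1, on placebo) + (later visit − Week 8, on ALXN2050).

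The ETP-baseline change is the second term alone.

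**3. Both errors are possible under the SAP rule of a QTcF increase above 30 msec.**

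- Placebo +35, ALXN2050 0: +35 from PEP (flagged), 0 from ETP (not flagged).
- Placebo −20, ALXN2050 +40: +20 from PEP (not flagged), +40 from ETP (flagged).

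**4. Illustration of size.** The documents give no SD, drift or drug effect, so all three are assumptions. Take one post-baseline visit, independent normal visit values and the same SD of change *s* from either baseline. Let *d* be the mean placebo-period drift and *e* the mean drug effect, both in msec.

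- From PEP: P(flag) = 1 − Φ((30 − e − d)/s)
- From ETP: P(flag) = 1 − Φ((30 − e)/s)

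| s (msec) | d = +10, e = 0: PEP | ETP | d = −10, e = +15: PEP | ETP |
|---|---|---|---|---|
| 10 | 2.3% | 0.1% | 0.6% | 6.7% |
| 15 | 9.1% | 2.3% | 4.8% | 15.9% |
| 20 | 15.9% | 6.7% | 10.6% | 22.7% |

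For s = 15 and d = +10, for example, 1 − Φ(20/15) = 9.1%. In 28 participants:

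- First scenario: between 28 × 0.022 = 0.6 and 28 × 0.092 = 2.6 extra flags.
- Second scenario: between 28 × 0.061 = 1.7 and 28 × 0.121 = 3.4 missed flags.

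With d = 0 the group rates agree (2.3% from either baseline at s = 15, e = 0). The individuals still differ: in a simulation of 1,000,000 draws, about 1.9% were flagged from each baseline alone.

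**5. Are the Week 8 values there?** Protocol Table 2 schedules ECG, vital signs, chemistry, hematology, coagulation, urinalysis, AP activity and Bb at Day 57. Protocol Table 3, footnote a, puts them before the first ALXN2050 dose: "The ETP begins at the Day 57 (Week 8) Visit after all assessments of the visit are performed". AP activity also has postdose samples that day, so only its predose sample qualifies. Weight is the exception: Table 2 lists it only at Screening, so the 7% weight criterion in SAP 5.6.1.3.2 has no scheduled Week 8 reference.

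**The case against.** The strongest reply is that a single pre-study baseline for every group is a legitimate prespecified choice. Day 1 and Day 57 predose are both free of ALXN2050 in the placebo group, and the SAP calls the PEP baseline primary even for efficacy. If mean drift on placebo is zero, group-level results are unbiased, and nothing in the documents shows any drift. This stands as a reason to keep the PEP-baseline tables. It does not remove the misclassification of individuals, nor the mixing of the two periods if there is drift.

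A reader might go further and infer that every safety change in Groups 3a/3b is misattributed, or that real ALXN2050 effects are hidden. The documents do not support that:

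- Treatment-emergent adverse events in these groups are dated from the first ETP dose (SAP 5.6.2.2). The Addendum reports adverse events and exposure separately for the PEP and for the ALXN2050-treated period.
- The limits of 450, 480 and 500 msec, and those for blood pressure, heart rate, temperature and respiratory rate, need no baseline.
- Absolute values by visit and by-participant listings are produced for laboratory, vital-sign, ECG and PD data. A reader can see Week 8 and work out the change from it, although no planned summary or count does so.

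It is also fair that the stakes have fallen. The study was stopped for lack of efficacy and will have one abbreviated report. The dual-baseline efficacy displays were exploratory and are dropped, and the retained MG-ADL and QMG descriptive summaries use the PEP baseline. The contrast with efficacy has therefore largely gone. The same facts mean that no ETP-baseline summary is specified for the final report.

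**Conclusion.** The point holds in a limited form. It covers change-from-baseline, shift and change-based outlier results for laboratory, vital-sign, ECG and PD data in Groups 3a/3b during ALXN2050 treatment. Followed as written, the plan combines placebo-period and on-drug change there.

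It touches up to about 28 of 70 participants. The group-level bias equals the mean change over the 8 placebo weeks. Its size and sign cannot be known from the documents, and it may be zero. The QTcF rates above depend wholly on assumed SDs, drifts and drug effects, and show only that errors of one to three participants in 28 are plausible in either direction. This is an inexpensive improvement worth making. It does not invalidate the safety assessment and has no bearing on the primary efficacy result.

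**What to change.** In SAP 5.1.1, 5.1.2, 5.6.1.3, 5.6.2, 5.7.2 and 5.9, or in a further addendum covering them:

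- For Groups 3a/3b, add an ETP-baseline version of the change, shift and QT/QTcF-increase tables for the ALXN2050 treatment period, and of PD change after Week 8. The baseline is the last value before the first ALXN2050 dose, normally Day 57 predose.
- Keep the PEP-baseline version alongside, and keep the PEP baseline for the placebo-period tables.
- Reconcile 5.1.2, 5.6.2, 5.7.2 and 5.9 with 6.1.2, so that the SAP says in one place which baseline applies to which data.
- Except the 7% weight criterion, and state in a footnote that no Week 8 weight is scheduled.

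Because the Week 8 results are already known, label the added tables as supplementary and date the decision to add them.

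The cost is SAP wording, one more baseline flag in the laboratory, vital-sign, ECG and PD datasets, and a second set of columns for two groups of about 14. No new data are needed.
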